(PHASE 2) For Phase 2, study staff will review upcoming scheduled appointments in the diabetes care center, and will screen the electronic medical records of scheduled patients for inclusion and exclusion criteria. Potentially eligible families will be sent an informational letter about the study, including instructions to contact study staff to learn more about the study or to opt-out of being contacted about the study. For families who do not opt-out, study staff will meet with them at the next scheduled diabetes clinic visit to confirm eligibility, describe the study protocol and risks in detail, and answer questions. Families who meet eligibility requirements and agree to participate will sign all required informed consent and assent forms and will receive a copy of the signed forms for their records.

During Phase 2, following consent and enrollment at the baseline clinic visit (V1), 82 adolescent-parent dyads will individually complete a questionnaire battery and will provide blood glucose meter for the staff to download data. They will also provide consent for study staff to review the patient's medical chart to document birth date, date of diagnosis, current insulin regimen, diabetes-related ER visits or hospitalizations, and most recent hemoglobin A1C - for the next 12 months.

Families will then be randomized using a 2:1 ratio to Group A or B (A=54, B=28). Group A will begin the intervention immediately. Research staff will provide verbal and written instruction on how to install and use the mobile phone app and will instruct families to begin using the app that day. Group B will be the control group for the entirety of the study and will receive usual care. At the V2 clinic visit (approx. month 3, or at the time of the next diabetes clinic visit), participants in Group A will stop using the app, and both groups will complete the questionnaire battery/provide meter for download again. At this time, Group A will provide qualitative feedback about their experiences and recommendations to improve the intervention. To assess the process of the intervention's impact, adolescents and parents in both groups will each provide biweekly ratings (via email, text message, or telephone) of their parent-adolescent relationship quality throughout the full study period (V1-V2).

Incentives will be distributed to participants following completion of each time point, as outlined in section L.

ASSESSMENTS:

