This sample size should be sufficiently large to conduct the qualitative and quantitative analyses to address the study aims and research questions. To allow for possible attrition or other loss of enrolled participants, we have added an additional 15% to our sample size estimate: $97 + 15 = 112$

G2. Data Analysis

Provide a description of your plan for data analysis. State the types of comparisons you plan (e.g. comparison of means, comparison of proportions, regressions, analysis of variance). Which is the PRIMARY comparison/analysis? How will the analyses proposed relate to the primary purposes of your study?

Qualitative Data (PHASES 1 and 2): Audio recordings will be transcribed verbatim by a medical transcription company and errors will be corrected prior to analysis. Thematic analysis will be used to analyze the qualitative data. Two coders will independently code and analyze the transcripts, and will discuss discrepancies to reach a joint coding resolution. The research team will meet throughout the coding and analysis process to discuss emerging themes and patterns. To protect confidentiality, transcripts will be coded by participant number not names.

Quantitative Data (PHASE 2) : Intervention feasibility will be determined if the upper bound of the 95% exact, binomial confidence interval (CI) is greater than or equal to 95% for downloading the app and greater than or equal to 70% for using the app at least twice per week. Acceptability will be measured as the proportion of participants who rate the intervention as acceptable (somewhat to very much) with 95% exact, binomial CIs (upper bound should be greater than or equal to 80%).

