The primary analysis of glycemic and behavioral outcomes will be to compare the change in response (V1 vs. V2) between groups using an independent, two-sample t-test. Equal variances will be assumed, unless the F test rejects the null hypothesis of equality. Quantile-quantile plots, stratified by group, will be used to test for approximate normality, and data transformations (e.g., natural logarithm) will be used if needed. All outcome measures will be independently compared between groups, and no adjustments for multiple hypothesis tests will be made in this pilot study. A general linear mixed model will also be used to compare groups and will allow for the use of all available data, including incomplete observations. The model will assume an unstructured matrix of correlated error terms to account for repeated observations. Statistical significance will be assessed at the 0.05 level for all hypothesis tests. A total sample size of $n=82$ with complete data would be required to detect an effect size of 0.75 with 80% power using an independent, two-sample t-test assuming $\alpha=0.05$. This sample size will also have >95% probability of generating binomial confidence intervals with half-widths ≤ 0.20 . Therefore, this study will plan to enroll $n=82$ (54 intervention, 28 control) in the pilot intervention trial (Phase 2) to allow for a 20% attrition rate.

Data from the second intervention period (V2) will be exploratory. A similar analysis will be used including independent, two-sample t-tests and general linear mixed models. Maintenance or drop-off of intervention engagement past three months will be observed for group A. Descriptive analyses of pre-post outcomes for both groups during the 3-month study period (V1-V2) will maximize this pilot sample's data to estimate trends and receive additional qualitative feedback.

Section H: Potential Risks/Discomforts

H1. Potential Risks/Discomforts

Describe and assess any potential risks/discomforts; (physical, psychological, social, legal, or other) and assess the likelihood and seriousness of such risks:

The risks associated with this study are relatively minor, as the protocol does not involve any medical procedures and the study procedures and intervention do not include any treatment or advice related to medical care of diabetes or treatment of psychological conditions. No study procedures or questions will

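### The primary change-score t-test leaves out every dyad without both visits; making the planned mixed model primary would guard against dropout that depends on baseline differently by arm

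*Combined protocol and SAP*

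**What the plan says.** Section G2 (Data Analysis) states that the primary analysis of glycemic and behavioral outcomes will "compare the change in response (V1 vs. V2) between groups using an independent, two-sample t-test". It then adds: "A general linear mixed model will also be used to compare groups and will allow for the use of all available data, including incomplete observations". On that model it specifies only the covariance: "The model will assume an unstructured matrix of correlated error terms to account for repeated observations". Fixed effects and the treatment contrast are not given.

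The same section enrols 82 dyads, 54 intervention and 28 control, "to allow for a 20% attrition rate". Section G1 uses another allowance for the whole study: "we have added an additional 15% to our sample size estimate". Neither section gives dropout by arm.

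G2 states no missing-data assumption, imputation rule or analysis population, and does not say which result counts if the t-test and the mixed model disagree.

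Section F2 affects how much will be missing. A1c is taken from the medical record, and meter data not obtained in person may be collected by email, fax or phone. No such route is described for the questionnaires.

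**The concern.** A change score cannot be formed without both visits, so the analysis labelled primary is complete-case by construction. The plan foresees incomplete data and includes a method that uses them, yet the headline result comes from the method that discards them.

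There are reasons to plan for dropout that works differently in the two arms. Only Group A uses the app. The F2 interviews ask about intrusiveness of the prompts, H1 accepts that the intervention could cause some distress, and Section L pays for data use by month of app use. If families with worse (or better) baseline values tend to leave one arm and not the other, the stayers in the two arms differ at baseline. Regression to the mean then gives them different expected changes even when the app does nothing. The headline estimate would mix that artefact with any true effect.

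**Working it through.** **1. The plan's own figure.** Inputs from G2: effect size 0.75, power 80%, alpha 0.05 (taken as two-sided; sidedness is not stated), two-sample t-test, 54:28 allocation, 20% attrition. A noncentral-t calculation at 2:1 needs 64.8 completers, so 65 (43 + 22, power 80.4%). Inflating for attrition: 65 / (1 − 0.20) = 81.25, so 82. The figure of 82 therefore reproduces as the number enrolled. It does not reproduce as the complete-data requirement, which is how G2 also describes it ("A total sample size of $n=82$ with complete data would be required to detect an effect size of 0.75 with 80% power"): 54 + 28 completers would give 88.9% power. Loss of power to the planned attrition is already covered.

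**2. Where bias comes from.** Standardise V1 and V2 to SD 1 with correlation r and no true effect.
- Expected change among stayers in one arm = −(1 − r) × (mean baseline of stayers).
- SD of change = √(2 − 2r): 1.00 at r = 0.5 and 0.775 at r = 0.7.
- Assume 20% dropout with log-odds rising by 1 per baseline SD. Integrating the logistic dropout curve over a normal baseline puts the stayers' mean baseline at −0.173 SD.
- If this occurs in Group A only: at r = 0.5 the bias is 0.5 × 0.173 = 0.087, or 0.087 SD of change. At r = 0.7 it is 0.3 × 0.173 = 0.052, and 0.052 / 0.775 = 0.067 SD of change.
- With the opposite slope in Group B the bias doubles, to 0.173 and 0.134.
- With the same slope and rate in both arms it cancels.

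The two-visit mixed model (unstructured covariance, separate arm-by-visit means) replaces the stayers' V2 mean by V2 mean of stayers + b × (V1 mean of all − V1 mean of stayers), where b is the slope of V2 on V1. That removes this term.

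**3. Simulation.** 54/28 dyads, V1 always observed, no true effect, 4,000 replicates per setting, slopes in log-odds per SD. Ranges are over r = 0.5 and 0.7; bias is in SDs of change. Correlations, slopes and arm-specific rates are assumptions. The 26%/8% split keeps overall loss near plan: (54 × 0.26 + 28 × 0.08) / 82 = 19.9%.

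| Dropout depends on | Rate A/B | t-test bias | t-test type I error | Mixed-model bias |
|---|---|---|---|---|
| Nothing | 20%/20% | within 0.01 | 4.6–5.9% | within 0.01 |
| Nothing | 26%/8% | within 0.01 | 4.8–5.0% | within 0.01 |
| Baseline, slope 1 in both arms | 20%/20% | within 0.01 | 5.0–5.5% | within 0.01 |
| Baseline, slope 1 in A only | 20%/20% | 0.06 to 0.08 | 6.0–6.9% | within 0.01 |
| Baseline, slope 1 in A only | 26%/8% | 0.08 to 0.12 | 6.2–7.6% | within 0.01 |
| Baseline, slope +1 in A, −1 in B | 20%/20% | 0.13 to 0.18 | 7.4–10.4% | within 0.01 |
| Unseen V2, slope 1 in A only | 20%/20% | −0.06 to −0.08 | 6.2–6.6% | −0.11 to −0.13 |
| Unseen V2, slope 1 in A only | 26%/8% | −0.08 to −0.11 | 6.2–8.2% | −0.15 to −0.17 |

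The simulated biases agree with step 2. A separate run with slopes of 1 to 1.5 in Group A, and 0 or −0.5 in Group B, gave 0.07 to 0.13 SD of change, inside the same range.

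**4. Scale.** 0.06 / 0.75 = 8% and 0.18 / 0.75 = 24% of the design effect. With 43 + 22 completers the standard error is √(1/43 + 1/22) = 0.26 SD, so the bias is about 0.2 to 0.7 of a standard error.

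**The case against.** The strongest reply is that this is a declared pilot whose stated purpose is feasibility, that the mixed model is already prespecified at the same level ("Statistical significance will be assessed at the 0.05 level for all hypothesis tests"), and that the choice of label is largely preference. The mechanism is also unproven. Both arms complete the questionnaires, meter downloads and biweekly ratings and are paid for them, V2 falls at the next routine clinic visit, and stopping the app is not leaving the study. The assumed slopes are strong: log-odds of 1 to 1.5 per SD are odds ratios of about 2.7 to 4.5.

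Much of this stands, and it rules out several stronger readings.
- A reader might infer that differing dropout between arms does bias the headline result. The documents report no such pattern, and a difference in rates alone (26% against 8%) produced no bias.
- A reader might infer that about 16 of 82 dyads (20%) leave every comparison. Loss is per outcome: A1c comes from the chart and meter data can be recovered remotely, so it will fall mainly on the questionnaires.
- A reader might infer that moving to the mixed model has no downside. When dropout in one arm depends on the unseen V2 value, the model was the more biased method. With two visits, a V1-only dyad adds baseline information only; its V2 is inferred under missing-at-random.

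The reply does not give a reason to prefer the complete-case test as primary. G2 names one analysis as primary and says nothing about what happens if the two disagree.

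**Conclusion.** The concern holds as a conditional risk. The primary t-test is complete-case for each outcome, with 20% attrition planned. If dropout depends on baseline differently by arm, it could be biased by roughly 0.06 to 0.18 SD of change, with type I error of about 6% to 10%, and the mixed model would be about unbiased. At the lower end the excess type I error is hardly separable from the 4.6% to 5.9% simulated when dropout was unrelated to outcome.

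These sizes rest on assumed correlations of 0.5 to 0.7 and log-odds slopes of about 1 to 1.5 per SD, none of which is in the documents. The advantage of the mixed model holds under missing-at-random and not beyond it. Sample size, power, and the feasibility and acceptability analyses are unaffected. The change is worth making because it is cheap and keeps more randomised dyads in the headline analysis.

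**What to change.** In G2, for the glycemic and behavioral outcomes:

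1. Name the mixed model as primary: all randomised dyads with at least one visit, analysed by assigned group; fixed effects of group, visit and group-by-visit; unstructured covariance; the group-by-visit term (difference in V1-to-V2 change) as the contrast. This keeps the t-test's target quantity.
2. State the missing-at-random assumption.
3. Keep the complete-case t-test as a sensitivity analysis.
4. Report missingness by arm and by outcome.
5. Add a simple delta-shift analysis for dropout that depends on V2. Shifting the missing V2 values in one arm by δ moves the contrast by δ times that arm's missing fraction; for example, 0.5 SD × 0.20 = 0.10 SD.
6. In the same edit, describe 82 as the number enrolled and about 65 as the completers required, and reconcile the 15% and 20% attrition figures. Also reconcile the later G2 statement that V2 data are exploratory with the primary V1-to-V2 comparison.

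The cost is a short text edit and one extra sensitivity analysis. No additional participants or data are needed, and N stays at 82. The remaining weakness is dropout driven by unobserved V2 values, which the delta-shift analysis displays but cannot remove.

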Phase 2: A two-group randomized design will be used to conduct the pilot intervention trial with n=82 adolescent-parent dyads. Participating families will be enrolled and randomized 2:1 to Group A-Intervention or B-Control (A=54, B=28). During the 3-month period, group A will receive the intervention while B serves as the control and receives usual care. Data collection will occur at baseline and approx 3 months (the 2nd data collection will occur at the subsequent diabetes clinic visit, which usually occur approximately every 3-4 months)

Inclusion Criteria:

Families will be eligible for both phases of the study if: 1) adolescent is between the ages of 12-17 years at enrollment; 2) receives treatment for T1D at Texas Children's Hospital (TCH); 3) T1D diagnosis of at least 6 months; 4) parent and adolescent exhibit fluency in reading/speaking English; & 5) parent has mobile device with a data plan.

Providers will be eligible for phase 1 if he/she: 1) provides treatment to adolescents (12 - 17 years old) with T1D, & 2) provides T1D treatment at one of the TCH diabetes clinics.

Exclusion Criteria:

Families will be excluded from both phases of the study if there is a serious medical, cognitive, or mental health comorbidity in parent or adolescent that would preclude ability to provide informed consent or participate in data collection or intervention. Families will be excluded from Phase 2 if they participated in Phase 1 or if they have participated in another intervention study in the previous 6 months prior to enrollment.

Providers will be excluded from Phase 1 if he/she is primarily a researcher or only providing treatment to non-T1D patients.

F2. Procedure

The study will be conducted in two phases.

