- Glycemic control measured by glycosylated hemoglobin A1c will be extracted from the medical record. A1c values are obtained in the course of routine clinical care in the TCH diabetes clinics.

(3) Intervention Process Measure (Study staff will collect ratings biweekly via email, telephone, or text message, during Phase 2)

- Parents and adolescents will each rate their relationship quality in relation to diabetes management using 3 items adapted from the Parent-Youth Relationship Index of the National Longitudinal Study of Youth-1997.

(4) Intervention Satisfaction and Feedback (Study staff will collect data for these measures following the intervention periods in both phases. - - Participants will complete the USE Questionnaire, a 32-item measure of the users' perceived usefulness of, satisfaction with, and ease of use of a particular technology.

- Semi-structured interviews with parents and adolescents in the intervention group will be conducted to contextualize survey responses, discuss user perspectives on the app (e.g., intrusiveness of prompts, clarity/relevance of response options, usefulness and appeal of strength behavior feedback charts), and obtain suggestions for improvement. The interviews will be conducted in person (in private meeting space) or over the telephone, whichever is most convenient for the family. The qualitative interviews will be audio-recorded and transcribed verbatim by medical transcriptionists for qualitative coding and analysis. The responses will inform future expansion of this study.

Section G: Sample Size/Data Analysis

G1. Sample Size

How many subjects (or specimens, or charts) will be used in this study?

Local: 112 Worldwide: 112

Please indicate why you chose the sample size proposed:

The purpose of this study is to develop and evaluate the feasibility of a strengths-based behavioral mHealth intervention for parents of adolescents with T1D, delivered via a smartphone app. In order to adequately capture the variability of experiences and preferences among adolescents with diabetes and their families, we propose to enroll a total of 97 participants, in the following way:

PHASE 1: 10 adolescent-parent dyads, 5 diabetes care providers PHASE 2: 82 adolescent-parent dyads

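### Section G2 gives 82 dyads as both the complete-data requirement and the enrolment that allows for 20% attrition; G1 then adds 15% to a total containing the same 82

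*Combined protocol and SAP*

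**What the plan says.** The power statement in section G2 (Data Analysis) reads: "A total sample size of $n=82$ with complete data would be required to detect an effect size of 0.75 with 80% power". It refers to an independent two-sample t-test at alpha 0.05. After one intervening sentence on confidence-interval width, the paragraph concludes that the study will "plan to enroll $n=82$ (54 intervention, 28 control) in the pilot intervention trial (Phase 2) to allow for a 20% attrition rate".

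Section G1 (Sample Size) builds a total of 97 from 10 Phase 1 dyads, 5 providers and "PHASE 2: 82 adolescent-parent dyads". To cover attrition or other loss of enrolled participants, it then says "we have added an additional 15% to our sample size estimate: $97 + 15 = 112".

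The number randomised is consistent throughout. F1 (Design) has "Participating families will be enrolled and randomized 2:1 to Group A-Intervention or B-Control (A=54, B=28"), F2 (Procedure) repeats the 54 and 28, and G2 agrees. That number is not in question.

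**The concern.** If 82 dyads with complete data are required, enrolling 82 leaves no room for loss: at 20% attrition 82 × 0.8 = 65.6 remain. If 82 already contains the allowance, it is not the complete-data requirement. One of the two sentences must be wrong, and no assumption is needed to see that.

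G1 adds a second difficulty. It treats 82 as an uninflated base and adds 15%, whereas G2 says 82 already allows for 20%. The plan therefore carries two attrition rates and does not say whether the additional 15% permits more than 82 dyads in Phase 2.

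This is the only power statement for what G2 calls the primary analysis of glycemic and behavioral outcomes. Taken literally, it says that any dropout leaves the trial short, or that enrolment should be 82/0.8 = 102.5, that is 103. A reader judging whether enough dyads completed the study would use the wrong threshold.

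**Working it through.** **Inputs from the documents**
- Test (G2): "compare the change in response (V1 vs. V2) between groups using an independent, two-sample t-test", with equal variances by default.
- Alpha (G2): "Statistical significance will be assessed at the 0.05 level for all hypothesis tests". G2 makes no multiplicity adjustment, so no smaller alpha applies.
- Effect size 0.75, power 80%, attrition 20% (G2).
- Allocation 54:28 (F1, F2, G2).
- Base of 97 and addition of 15% (G1).

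**Assumptions, because the text does not state them:** the test is two-sided, and 0.75 is in units of the standard deviation of the change score (no standard deviation is given).

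**Formula.** For group sizes n₁ and n₂, the noncentrality is δ = 0.75 / √(1/n₁ + 1/n₂) on n₁ + n₂ − 2 degrees of freedom. Power is the probability that a noncentral t variable exceeds the two-sided 5% critical value in absolute size.

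**Step 1. Try to reproduce 82 as the complete-data requirement.** With 54:28, δ = 0.75 / √(1/54 + 1/28) = 3.22 on 80 degrees of freedom, critical value 1.99. Power is 88.9%. The effect detectable at 80% power is 0.66, not 0.75. The stated figure does not reproduce.

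**Step 2. Find the number of complete dyads that gives 80%.**

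| Complete dyads | Split | Power |
|---|---|---|
| 63 | 42:21 | 78.9% |
| 64 | 42:22 | 80.1% |
| 65 | 43:22 | 80.4% |
| 66 | 44:22 (exactly 2:1) | 80.8% |
| 82 | 54:28 | 88.9% |

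For 43:22, δ = 0.75 / √(1/43 + 1/22) = 2.86 on 63 degrees of freedom, and the effect detectable at 80% power is 0.746.

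**Step 3. Apply the 20% loss.** 54 × 0.8 = 43.2 and 28 × 0.8 = 22.4, so about 43:22 remain, with 80.4% power. In the other direction, 65/0.8 = 81.25, which rounds up to 82. The figure 82 therefore reproduces as the enrolment after allowing for attrition.

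**Step 4. Check whether another reading rescues 82.**
- 1:1 allocation, two-sided: 58 (29:29, 80.1%).
- 2:1 allocation, one-sided 0.05: 51 (34:17, 80.1%).
- Normal approximation, two-sided: 63 at 2:1, 56 at 1:1.
- For 54:28 to give only 80% power at 0.75, two-sided alpha would have to be 0.020, against the stated 0.05.

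None of these gives 82 at alpha 0.05.

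**Step 5. Check power at the other stated loss rate.** 82 × 0.85 = 69.7, about 46:24, with power about 83.5%.

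**Step 6. Split the G1 addition.** 97 × 0.15 = 14.55, and 97 + 14.55 = 111.55, rounded to 112. Of the 14.55, 82 × 0.15 = 12.3 comes from Phase 2 and 15 × 0.15 = 2.25 from the 15 Phase 1 units (10 dyads and 5 providers). Applied to Phase 2 alone, 15% would give 82 × 1.15 = 94.3, against 82 in F1, F2 and G2.

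**Step 7. Check the neighbouring sentence in G2** on confidence-interval half-widths of at most 0.20. In Group A the largest exact 95% half-width is 0.139 with 54 and 0.156 with 43, so that sentence survives the correction.

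**The case against.** The strongest reply is that nothing in the conduct of the trial turns on this. It is a pilot aimed at feasibility, judged by confidence-interval bounds. The mixed model uses incomplete observations, and no decision rule refers to a number of completers. It is true that the trial is not underpowered and that enrolment need not change. But the plan chose to give a power-based requirement, and the figure it gives is wrong.

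A second reply is that the two allowances may serve different purposes: 20% for dropout after randomisation in Phase 2, and 15% for study-wide losses, including between consent and randomisation, with 112 as a ceiling. The documents do not say this. F2 has the 82 dyads consented and enrolled before the baseline battery and randomisation, and G2 puts enrolment itself at 82, so there is no larger enrolled pool from which 82 are randomised. A ceiling would be acceptable if it were labelled as one.

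A third reply is that 65 is inferred. This stands in part: 64 (42:22) already reaches 80.1% and would inflate to 64/0.8 = 80, while exactly 2:1 needs 66, which inflates to 82.5, or 83. The figure should be given as approximate, and the sponsor should confirm it against its own calculation. Nothing in the range 64 to 66 supports 82 as the complete-data requirement.

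**Conclusion.** The concern holds. The two uses of 82 in G2 contradict each other on their face. Under a two-sided alpha of 0.05, a standardised effect of 0.75 and roughly 2:1 allocation, the complete-data requirement is about 65 dyads, 17 fewer than stated (82 − 65). The power attached to 82 complete dyads is 88.9% rather than 80%. The wrong words are those that call 82 a complete-data figure; its use as the enrolment target is sound.

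G1 compounds the error by applying a different rate, 15%, to a total of which 82 already carries the 20% allowance; 12.3 of the 14.55 added falls on that 82.

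This is an error in a stated figure and not a shortfall in power. It would be wrong to conclude that 103 dyads must be enrolled.

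**What to change.** Restate the sentence in G2 along these lines: about 65 dyads with complete data (43:22) give 80% power at two-sided alpha 0.05 for a standardised effect size of 0.75; 82 dyads (54:28) are enrolled to allow for 20% attrition. The sponsor should confirm the sidedness, the standardisation and the number of complete dyads from its own calculation.

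In G1, state that 82 is the number randomised in Phase 2 and already includes attrition, and do not apply the 15% to it. If 112 is kept as a study-wide ceiling, say so, and say that it does not raise the number randomised.

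The cost is wording in two sections. The 82 dyads, the 54:28 split, the test and alpha stay as they are, and no extra participants are needed. If the sponsor confines the 15% to Phase 1 instead of keeping 112 as a ceiling, the declared total falls to 97 + 2.25 = 99.25, about 100, and the subject count in G1 must be updated to match.
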